5.3.3 Guidance on Assessment of Cardiovascular Events

A Clinical Event Committee (CEC) blinded to the treatment of the subjects, will independently adjudicate certain cardiovascular adverse events, and they will operate in accordance with a dedicated Clinical Event Committee Charter/Manual of Operations.

Events related to the following will be sent to the CEC for adjudication:

- Death, including:
 - Cardiovascular Death
 - Non-cardiovascular Death
- Myocardial Infarction (MI), including:
 - ECG and/or cardiac enzymes confirmed MI
 - Sudden death
 - Percutaneous Coronary Intervention (PCI)-related MI
 - Coronary Artery Bypass Graft (CABG)-related MI
 - MI diagnosed via pathologic criteria
 - Silent MI

- Fatal and Non-fatal Stroke, including:
 - Ischemic Stroke
 - Hemorrhagic stroke
- Serious Adverse Events of the following:
 - Heart failure
 - Cardiac arrhythmia
 - Unstable angina
 - Unplanned arterial revascularization (coronary, carotid and peripheral)
 - Cardiac arrest with successful resuscitation
 - Deep vein Thrombosis and Pulmonary Emboli
 - Systemic non-stoke arterial embolism/thrombosis including systemic arterial occlusion
 - Non-traumatic amputation of the lower limb. Only events above the ankle will be considered for adjudication.

In order to provide the independent CEC with appropriate and adequate information for adjudication of the listed events, please consult the Reference Manual Adjudication Reference Manual for Primary Investigators and Study Staff.

5.3.4 Guidance on Assessment of Hepatic Laboratory Abnormalities

An independent Hepatic Adjudication Committee, blinded to the treatment of the subjects, will determine the probability that drug-induces liver injury (DILI) is the cause of liver-related abnormalities, included, but not limited to:

- Hepatic disorders leading to discontinuation from study treatment and/or death
- Liver laboratory abnormalities such as elevated AST and/or ALT with or without TB elevations

A separate Adjudication Manual will define and describe the procedure for the handling, reporting and classification of these cases.

The following is presented to assist in the evaluation and management of hepatic laboratory values. It is not intended to supplant Investigators' clinical judgment.

Subjects who experience ALT and/or AST values >3x ULN confirmed with a repeated test will have the following performed within 3 days of the confirmed laboratory results:

- AE assessment
- Physical examination for jaundice and other signs of liver diseases
- Review of relevant risk factors and current history focusing on possible causes of the increased ALT and/or AST and/or TB, including:
 - Use of suspect concomitant medication [including over-the-counter (ie acetominaphen/paracetamol), herbal and vitamin preparations]
 - Recent alcohol consumption or recreational drug/narcotic use
 - Recent unaccustomed physical exertion
 - Occupational or environmental exposure to hepatotoxins
 - Other conditions which may cause liver diseases or which may cause abnormal test results
- Specialized liver laboratory panel (see Appendix 2)

Additional information, including but not limited to completion of supplemental eCRF's, or questionnaires may be requested for certain adverse events and/or laboratory abnormalities which are reported/identified as part of the hepatic safety surveillance.

For subjects who are discontinued from the study medication as a result of sustained elevated liver safety abnormalities as described in Section 3.5, additional blood sampling must be done within 3 days of the confirmed laboratory results (see Appendix 5), in conjunction with an Early Treatment Discontinuation (End-of-Treatment) visit, in addition to the procedures noted above. A referral consultation to a hepatologist or gastroenterologist (specializing in liver abnormalities) should be obtained. Any additional tests and/or examinations should be carried out at the discretion of the Investigator. Any further investigations and laboratory results for subjects with abnormal laboratory values at the follow-up visit should be made available to the Sponsor upon request.

5.3.5 Physical Examination

- A brief physical examination should include cardiovascular, lungs, abdomen, and extremities, and any organ systems pertinent to the subject's signs, symptoms, or adverse events
- A full physical examination should include general appearance, head, eyes, ears, nose, throat, neck, cardiovascular, lungs, abdomen, lymph nodes, extremities, neurological, skin, and musculoskeletal.

The individual performing the physical examinations must be licensed by state law (or applicable local law) to perform this procedure.

5.3.6 Blood Pressure and Heart Rate

Blood pressure (BP) and heart rate (HR) measurements must be taken consistently throughout the study. Only use either the right or the left arm when measuring these parameters. Document which arm was used along with the observer's initials; the same arm should be used for each position and at each visit. The subject should be allowed at least 5 minutes of rest before measurement. Seated blood pressure should be measured with the subject's arm resting on a table, and with subject's back support and feet flat on the floor.

Seated BP and HR will be determined from three replicate measurements obtained at least 1 minute apart. The average BP and HR will be determined from these 3 replicate measurements and reported in the eCRF.

All measurements should occur at least 8 hours after the last ingestion of caffeine, alcohol, or nicotine.

It is critical that the blood pressure and heart rate measurements be obtained prior to the administration of blinded study medication.

5.3.7 Liquid Meal Tolerance Test (MTT)

MTTs are scheduled to occur at Day 1 visit and at Week 24 / Study Termination visit, or Rescue/ETD visit for subjects meeting criteria for rescue due to lack of glycemic control. A maximum of 2 MTTs will be performed per subject: one at the Day 1 visit and the other at either the Week 24 / Study Termination visit, or Rescue/ETD, whichever occurs first.

The MTT visit should be rescheduled within 3 days if the subject did not comply with all of the following:

- Subject fasted for at least 8 h prior to the visit
- Subject abstained from tobacco, alcohol, and caffeine for 8 h prior to the MTT.

Note: In the event more than 2 time points are missing from the Day 1 MTT, the Investigator should contact the Medical Monitor prior to proceeding with the Week 24 /

Study Termination visit, or Rescue/ETD, as there might be situations where the analysis cannot be performed in the absence of key time point expected to be obtained at Day1. In these situations, conducting a MTT at Week 24 / Study Termination visit, or Rescue/ETD may not be required.

At Day 1 (randomization), study medication is given within 2 hours AFTER MTT is complete.

- Insert saline lock, if appropriate
- Draw Time 0 blood sample for glucose, insulin, C-peptide and glucagon
- Administer the liquid meal supplement over 10 minutes, starting immediately after Time 0 blood sample is drawn
- Draw specimens for post-liquid meal glucose, insulin, C-peptide and glucagon at 30, 60, 120, and 180 minutes
- Give study medication within 2 hours **AFTER** MTT is complete.

At Week 24/Study Termination Visit (or at Rescue Visit/ETD visit), the study medication is given 1 hour BEFORE administration of the liquid meal supplement.

- Insert saline lock, if appropriate
- Draw Time -60 minutes BEFORE taking study medication
- Give study medication 1 hour BEFORE administration of the liquid meal supplement
- Draw Time 0 blood sample for glucose, insulin, C-peptide and glucagon
- Administer the liquid meal supplement over 10 minutes, starting immediately after Time 0 blood sample is drawn
- Draw specimens for post-liquid meal glucose, insulin, C-peptide and glucagon at 30, 60, 120, and 180 minutes.
- Remove saline lock.

In the event an MTT is performed during the course of a Rescue visit, first dose of rescue medication should be taken after completion of the MTT.

5.3.8 Supplemental Visits

5.3.8.1 Rescue or Early Treatment Discontinuation Visit

Subjects rescued during or discontinued from the Double-Blind Treatment Period

Any subject who qualifies for rescue or discontinues from the Double-Blind Treatment Period must have all Rescue/Early Treatment Discontinuation (ETD) visit procedures performed at the time of study drug discontinuation or rescue. The IVRS must be called to record the subject status (ie, rescue, or discontinuation status). All subjects who are rescued or who discontinue study drug should remain in the study and follow the visit schedule.

- For subjects qualifying for rescue **PRIOR** to Week 24, Rescue/ETD procedures will be performed and the subject will then continue in the study according to the regular visit schedule. The Rescue/ETD supplemental eCRF will need to be completed to collect Rescue related endpoint data. A WK24/Rescue/ETD visit laboratory kit will need to be used to collect Rescue Visit blood and urine samples
- Subjects who discontinue study medication during the double-blind treatment period should have all ETD procedures performed (Rescue/ETD visit). The Rescue/ETD supplemental eCRF will also need to be completed and a Week 24/Rescue/ET visit laboratory kit will need to be used to collect ETD Visit blood and urine samples. The subject will then continue in the study according to the regular visit schedule.

5.3.8.2 Other Supplemental (Unscheduled Visits)

At any time during the trial, the Investigator may at his/her discretion arrange for a subject to have an unscheduled (supplemental) assessment(s), especially in the case of AEs that require follow-up. If a subject is seen for an unscheduled assessment, the appropriate Supplemental Pages of the eCRF must be completed.

5.4 Efficacy Assessments

Efficacy assessments consist of the central laboratory measurement of the HbA1C during the treatment period and the FPG, 2-hour post-liquid meal plasma glucose, insulin, C-peptide and glucagon throughout the treatment period.

Other efficacy assessments will also include the mean change from baseline in body weight at Week 24 with the addition of saxagliptin and dapagliflozin to metformin vs. the addition of placebo and saxagliptin to metformin.

5.5 Pharmacokinetic Assessments

Not applicable.

5.6 Biomarker Assessments

Blood will be collected on Day 1 and Week 24 to assess the effects of saxagliptin and dapagliflozin added to metformin after 24 weeks of double-blind treatment on stromal cell-derived factor-1 (SDF-1), a chemokine related to cardiovascular disease which attracts endothelial progenitor cells and induces angiogenesis.

5.7 Outcomes Research Assessments

Not applicable.

5.8 Other Assessments

5.8.1 Diet and Exercise Counseling

Starting at the lead-in period, subjects will be instructed on a diet and an exercise program in accordance with the ADA or similar local guidelines to be followed for the study duration.

A Registered Dietitian, Registered Nurse, Physician, Certified Diabetes Educator, Nutritionist, or other qualified member of the study team who has appropriate documented training will provide this counseling.

In addition, as part of the diet and exercise program, the Investigator or designee should ensure that each subject receives an adequate daily intake of calcium and vitamin D, in accordance with the National Academy of Sciences or similar local guidelines.

5.8.2 Height and Body Mass Index (BMI)

- Measurement of height should be performed with the subject's shoes removed. The subject's knees should be straightened, head held erect, and eyes forward.
- BMI is used as an index of obesity and is a method of defining normal body weight and excess body fat. It correlates in a population with percent body fat.
- BMI is determined by weight (kg) divided by height (m) squared

Method of BMI Calculation:

- Use actual height and weight to calculate BMI.
- To calculate BMI:
 - Convert pounds (lbs) to kilograms (kg = lb / 2.2)
 - Convert inches (in) to centimeters (cm=in x 2.54)
 - BMI = (weight in kg) / (height in cm/100)²
 - Round to one decimal place (if .05 or greater, round up)

5.8.3 Waist Circumference

The waist circumference measurements will be performed at various time points during the course of the study (refer to Table 5.1). They will be measured by placing a measuring tape midway between the lower rib and iliac crest. The measuring tape should pass over the umbilicus. The waist measurement reported on the eCRF should represent the average of at least 2 measurements. The average measurement should agree with 1 cm. If not, additional measurement(s) should be taken.

5.8.4 Survey of Subject Vital Status

Subjects who prematurely discontinue from the study may be contacted after discontinuation from the study, to collect vital status information.

5.9 **Results of Central Assessments**

Blood and urine samples will be obtained at specified time points for laboratory evaluations (see Appendix 2). The central laboratory for this study will perform the analysis of all scheduled laboratory tests and will provide reference ranges for these tests.

During the lead-in and double-blind treatment periods, the HbA1C, plasma glucose and insulin MTT values, and the urinary glucose values, including the urinary glucose:creatinine ratio will be masked to the Investigator and to the Sponsor. These values will be provided to the Investigator after the study has been completed.

6 ADVERSE EVENTS

An *Adverse Event* (*AE*) is defined as any new untoward medical occurrence or worsening of a pre-existing medical condition in a patient or clinical investigation subject

administered an investigational (medicinal) product and that does not necessarily have a causal relationship with this treatment. An AE can therefore be any unfavorable and unintended sign (including an abnormal laboratory finding, for example), symptom, or disease temporally associated with the use of investigational product, whether or not considered related to the investigational product.

Adverse events can be spontaneously reported or elicited during open-ended questioning, examination, or evaluation of a subject. (In order to prevent reporting bias, subjects should not be questioned regarding the specific occurrence of one or more AEs.)

6.1 Serious Adverse Events

A serious AE (SAE) is any untoward medical occurrence that at any dose:

- results in death
- is life-threatening (defined as an event in which the subject was at risk of death at the time of the event; it does not refer to an event which hypothetically might have caused death if it were more severe)
- requires inpatient hospitalization or causes prolongation of existing hospitalization (see **NOTE** below)
- results in persistent or significant disability/incapacity
- is a congenital anomaly/birth defect
- is an important medical event (defined as a medical event(s) that may not be immediately life-threatening or result in death or hospitalization but, based upon appropriate medical and scientific judgment, may jeopardize the subject or may require intervention [eg, medical, surgical] to prevent one of the other serious outcomes listed in the definition above.) Examples of such events include, but are not limited to, intensive treatment in an emergency room or at home for allergic bronchospasm; blood dyscrasias or convulsions that do not result in hospitalization.) Potential drug induced liver injury (DILI) is also considered an important medical event. (See Section 6.6 for the definition of potential DILI.)

Suspected transmission of an infectious agent (eg, any organism, virus or infectious particle, pathogenic or non-pathogenic) via the study drug is an SAE.

Although pregnancy, overdose, cancer, and potential drug induced liver injury (DILI) are not always serious by regulatory definition, these events must be handled as SAEs. (See Section 6.1.1 for reporting pregnancies).

NOTE:

The following hospitalizations are not considered SAEs in BMS clinical studies:

- a visit to the emergency room or other hospital department < 24 hours, that does not result in admission (unless considered "important medical event" or event life threatening)
- elective surgery, planned prior to signing consent
- admissions as per protocol for a planned medical/surgical procedure
- routine health assessment requiring admission for baseline/trending of health status (eg, routine colonoscopy)
- medical/surgical admission for purpose other than remedying ill health state and was planned prior to entry into the study. Appropriate documentation is required in these cases
- admission encountered for another life circumstance that carries no bearing on health status and requires no medical/surgical intervention (eg, lack of housing, economic inadequacy, care-giver respite, family circumstances, administrative).

6.1.1 Serious Adverse Event Collection and Reporting

Following the subject's written consent to participate in the study, all SAEs, whether related or not related to study drug, must be collected, including those thought to be associated with protocol-specified procedures. All SAEs must be collected that occur during the screening period and within 30 days of discontinuation of dosing. The investigator should report any SAE occurring after these time periods that is believed to be related to study drug or protocol-specified procedure. An SAE report should be completed for any event where doubt exists regarding its status of seriousness.

If the investigator believes that an SAE is not related to study drug, but is potentially related to the conditions of the study (such as withdrawal of previous therapy, or a complication of a study procedure), the relationship should be specified in the narrative section of the SAE Report Form.

SAEs, whether related or not related to study drug, and pregnancies must be reported to BMS (or designee) within 24 hours. SAEs must be recorded on the SAE Report Form; pregnancies on a Pregnancy Surveillance Form (electronic or paper forms). When using paper forms, the reports are to be transmitted via email or confirmed facsimile (fax) transmission to:

SAE Email Address: See Contact Information list.

SAE Facsimile Number: See Contact Information list.

For studies capturing SAEs/pregnancies through electronic data capture (EDC), electronic submission is the required method for reporting. The paper forms should be used and submitted immediately, only in the event the electronic system is unavailable for transmission. When paper forms are used, the original paper forms are to remain on site.

SAE Telephone Contact (required for SAE and pregnancy reporting): See Contact Information list.

If only limited information is initially available, follow-up reports are required. (Note: Follow-up SAE reports should include the same investigator term(s) initially reported.)

If an ongoing SAE changes in its intensity or relationship to study drug or if new information becomes available, a follow-up SAE report should be sent within 24 hours to the BMS (or designee) using the same procedure used for transmitting the initial SAE report.

All SAEs should be followed to resolution or stabilization.

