3.5 Discontinuation of Subjects from Treatment

Subjects MUST discontinue investigational product (and noninvestigational product at the discretion of the investigator) for any of the following reasons:

- Withdrawal of informed consent (subject's decision to withdraw for any reason)
- Any clinical adverse event (AE), laboratory abnormality or intercurrent illness which, in the opinion of the investigator, indicates that continued participation in the study is not in the best interest of the subject
- Pregnancy
- Termination of the study by Bristol-Myers Squibb (BMS)
- Loss of ability to freely provide consent through imprisonment or involuntary incarceration for treatment of either a psychiatric or physical (eg, infectious disease) illness
- $eGFR < 60 \text{ mL/min/}1.73 \text{m}^2$ for sustained period of time (12 16 weeks)

Dapaglifozin based on its mechanism of action has been shown to reduce eGFR by up to 10% with initiation of therapy; however this has in general been reversible and not resulted in renal failure and eGFR values returned to baseline within 12 - 24 weeks of continued therapy.

In case of a decision to discontinue treatment the Investigator will follow the subject until the event has resolved or stabilized, however at least till week 24.

All subjects who discontinue from treatment should comply with protocol specified follow-up procedures as outlined in Section 5. The only exception to this requirement is when a subject withdraws consent for all study procedures or loses the ability to consent freely (ie, is imprisoned or involuntarily incarcerated for the treatment of either a psychiatric or physical illness).

If a subject was withdrawn before completing the study, the reason for withdrawal must be entered on the appropriate case report form (CRF) page.

In addition, subjects who prematurely discontinue from the study may be contacted, after discontinuation from the study, to collect vital status information.

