5.3.2.2 Guidance on Assessment of Hematuria

All events of hematuria (confirmed by microscopy) during the double blind phase of the study should be investigated according to local standards and best clinical practices for a possible cause. If an immediate or benign common cause is identified eg., menstruation, urinary tract infection (UTI) the cause should be treated and resolution be confirmed and documented with a microscopic urinary analysis (performed by central laboratory) at an unscheduled visit while the patient continues in the study (See appendix 3).

If **NO** common cause is identified, if a malignancy is otherwise suspected or positive hematuria (by microscopy) at the unscheduled repeat visit is found this should be captured on the nonserious AE CRF page or SAE page, as appropriate, (See section 6.3) and the supplemental hematuria CRF page, and patients should be further investigated based on American Urological Association (AUA) guidelines or equivalent local standard of care and best practices which could include referral to an urologist and undergoing evaluation that may include abdominal computed tomography (CT), urine cytology, and NMP-22 urine test. The patient should continue to receive investigational product treatment during these investigations (unless otherwise contraindicated).

It is the investigator's responsibility to report, as applicable based on Investigator's judgment and subject's medical history, related adverse events as defined in Section 6. Additional information, including but not limited to completion of supplemental eCRFs or questionnaires may be requested for certain adverse events and/or laboratory abnormalities which are reported/identified during the course of the study.

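### The period for collecting SAEs regardless of relationship closes 30 days after dosing stops, which conflicts with off-drug follow-up to Week 24

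*Protocol*

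**What the plan says.** Section 6.1.1 deals with the SAE period in three sentences.

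- The first starts at written consent and says that "all SAEs, whether related or not related to study drug, must be collected, including those thought to be associated with protocol-specified procedures". It gives no end date.
- The second names a period: "All SAEs must be collected that occur during the screening period and within 30 days of discontinuation of dosing".
- The third covers what comes later: "The investigator should report any SAE occurring after these time periods that is believed to be related to study drug or protocol-specified procedure".

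Other sections keep subjects under observation after they stop drug. Section 3.5 has the investigator follow them "until the event has resolved or stabilized, however at least till week 24". Section 5.3.8.1 adds: "All subjects who are rescued or who discontinue study drug should remain in the study and follow the visit schedule". Table 5.1 marks adverse event assessment at Weeks 6, 12, 18 and 24 with no note restricting it to subjects on drug. Its last scheduled visit is Week 24/Study Termination.

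Section 5.3.3 says "Events related to the following will be sent to the CEC for adjudication". Its list includes deaths of any cause, myocardial infarction and stroke, with no limit relative to the last dose. Section 6.1 requires cancer to be handled as an SAE.

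**The concern.** The mandatory SAE period follows the dosing date, while observation of the subject follows the calendar to Week 24. A subject who stops early attends visits and is asked about adverse events, yet more than 30 days after the last dose the site can conclude that an SAE it judges unrelated need not be reported. The site's opinion on causality then decides whether a death, myocardial infarction, stroke or cancer reaches the sponsor and, for the listed events, the blinded committee set up to judge them independently.

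The result is also uneven. Section 6.2.1 requires all identified nonserious events to be recorded and states no end date. A minor complaint at Week 18 would be recorded, while the duty to report an unrelated stroke found at the same visit is unclear. Section 1.5 acknowledges that the safety of this combination is not yet established, so complete ascertainment of serious events matters.

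**Working it through.** The plan gives no figure to reproduce. The check is day arithmetic followed by a comparison of the texts.

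**Inputs.** Week 24 is day 24 × 7 = 168 (synopsis, 24-week double-blind period). The window is 30 days after dosing stops (6.1.1). Follow-up after stopping runs at least to Week 24 (3.5, 5.3.8.1). Let s be the day dosing stops.

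**Formulas.** The window closes on day s + 30. Attended follow-up outside it is max(0, 168 − (s + 30)), out of 168 − s off-drug days. The part of the window after the last visit is max(0, s + 30 − 168).

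| Dosing stops | Window closes | Off-drug days to Week 24 | Days outside window | Share |
|---|---|---|---|---|
| Day 1 | Day 31 | 167 | 137 | 82% |
| Week 6 (day 42) | Day 72 | 126 | 96 | 76% |
| Week 12 (day 84) | Day 114 | 84 | 54 | 64% |
| Week 18 (day 126) | Day 156 | 42 | 12 | 29% |
| Day 138 | Day 168 | 30 | 0 | 0% |

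The gap vanishes when s + 30 = 168, so s = 138, and 138/7 = 19.7 weeks. A visit window of ±5 days moves this to between day 133 and day 143.

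**Example.** A subject stops at Week 6, so the window closes on day 72. The Week 12, 18 and 24 visits (days 84, 126 and 168) all fall later. A stroke at Week 16 (day 112), judged unrelated, would come to light at the Week 18 visit. Under the first sentence of 6.1.1 it must be collected. Under the second and third it need not be reported.

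**Which sentence governs.** If the first sentence applied without limit, the third would have no work to do, because related SAEs after the period would already be covered. The third sentence therefore implies that unrelated SAEs drop out once the 30 days have passed. The second sentence, read alone, does not even name the treatment period, so it cannot be the whole rule either. The three sentences do not give one answer.

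**Scale, on an assumption.** The protocol states no stopping rate. If 5% to 10% of the 516 planned subjects stopped, all at Week 8 (day 56), the gap for each is 168 − 86 = 82 days. That gives 25.8 × 82/365.25 = 5.8 to 51.6 × 82/365.25 = 11.6 person-years. These subjects are still attending visits, so this is time with an unclear reporting duty and not time unobserved.

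**Completers.** With s = 168 the window closes on day 198, and all 30 days fall after the last visit in Table 5.1. The vital-status contact in 3.5 and 5.8.4 is optional and applies only to subjects who leave the study prematurely.

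**The case against.** The strongest reply is that 6.1.1 opens by requiring all SAEs after consent, so the later sentences add to that duty and do not cut it. The subject in the example attends Week 18 and is asked about adverse events, section 5.3.3 has no time limit, and related SAEs stay reportable indefinitely. Dosing plus 30 days is also a recognised on-treatment window, and which off-drug events enter the tables can be left to the SAP.

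Part of this stands. Collection does not simply end at 30 days, and the event would probably be seen. But the third sentence undercuts the open-ended reading, and sites can reasonably differ. An SAP can select among collected events. It cannot restore events that were never reported.

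A reader might infer several stronger things that the protocol does not support:

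- **That serious events are missed.** They can go unreported; nothing shows that they do.
- **That the comparison between arms is biased.** No difference in stopping by arm is shown, and the gap after Week 24 is the same in all three arms.
- **That subjects who stopped for an adverse event are the least covered.** The window depends on the date of stopping and not the reason, and 3.5 follows these subjects at least to Week 24.
- **That completers have no contact at all.** Only a scheduled contact is absent. SAE reporting stays mandatory in those 30 days, and 6.1.1 and 6.2.1 follow known events to resolution or stabilization. Counting the 30 days as lost person-years would be wrong.
- **That hematuria found at Week 24 is left unhandled.** Appendix 3 covers that visit, and its algorithm is a figure missing from the text available here.

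**Conclusion.** The protocol contradicts itself on whether unrelated SAEs must be reported for subjects who are off drug but still in the study. The conflict affects anyone stopping before about day 138. The share of attended off-drug time outside mandatory collection falls from 82% for a day 1 stop to 29% for a Week 18 stop. The consequence is ascertainment that can vary by site and by stopping time; its effect on the arms depends on stopping rates that the protocol does not give. The point should be corrected but does not threaten the primary analysis.

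The gap for completers is secondary. The 30-day duty exists, but it relies on spontaneous reporting. That conclusion rests on Table 5.1 and the text, because the study design figures were not available.

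**What to change.** In section 6.1.1, replace the three sentences on the period with one rule: all SAEs, regardless of relationship, are collected from consent to the later of 30 days after the last dose and the subject's Week 24/Study Termination visit. Keep the existing provision for related SAEs after that. The cost is protocol wording and a few more SAE reports, since these subjects already attend the visits.

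As a secondary change, add to Table 5.1 one telephone contact about 30 days after the last dose for subjects dosed to Week 24, to ask about SAEs and vital status. The cost is one call per completer and closure of the safety data about 30 days later.
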